13.8.6. Focused Ears, Nose, and Throat (ENT)/Eye Examinations

Descriptive statistics will be used to summarize ENT/eye results and changes from baseline by treatment group and time. The number of subjects with findings of potential clinical significance will be tabulated. All ENT/eye data will be displayed in listings.

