9. SAFETY AND TOLERABILITY

9.1. Overall Summary of Tolerability

The safety analyses will be based on the SAS, unless otherwise specified. If a subject is randomized in the study more than one time, it will be decided at the Blind Data Review Meeting (BDRM) or after unblinding, on a case by case basis if the subject is counted in the numerator of any specific safety analysis.

Table 6 provides an overview of the planned analyses.

Table 6: Overview of Planned Safety Analyses

Display Type	Data Displays Generated		
	Table	Figure	Listing
Adverse Events			
Overview	Y[2]		
Treatment Emergent AEs	Y[1][2]		Y
Treatment Emergent AEs Severity	Y[2]		Y
Treatment-Related Emergent AEs	Y[2]		Y
Placebo Run-In Period AEs	Y[2]		Y
Pre-run-in period AEs			Y
AEs Leading to Withdrawal			Y
SAEs	Y[2]		Y
Treatment Emergent SAEs	Y[2]		Y
Treatment Emergent SAEs Severity	Y[2]		Y
Treatment-Related Emergent SAEs	Y[2]		
Laboratory			
Pregnancy Test Results			Y
Other			
Vital Signs	Y[3] [2]		Y
Physical Examination	Y[4] [2]		Y
Focused ENT Examination	Y[5] [2]		Y

NOTES :

- Y = Yes display generated.
- [1]: Display will also be produced by SOC, severity, and by relationship to study medication
- [2]: Display will be based on safety analysis set
- [3]: Display will be produced separately for overall summary (inc. change from baseline), for potentially clinically significant results, and shift tables
- [4]: Display will be produced separately for overall summary
- [5]: Display will be produced separately for overall summary and for potentially clinically significant results

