9.8. Focused ENT/Eye examination

Post-baseline focused ENT/Eye examinations will be performed at Visits 3 and 4.

Descriptive statistics (frequency and percentage) will be used to summarize ENT/Eye examination results by treatment group and visit. In addition, the number of subjects with values of potential clinical significance determined by the investigator will be tabulated.

The focused ENT exam reviews the following 9 symptoms: Nasal irritation, Epistaxis, Mucosal Edema, Nasal Discharge, Mucosal Erythema, Crusting of Mucosa, Throat Irritation, Candidiasis, Post Nasal Drip. A severity grade of “None” is collected on the CRF and considered as a normal value; more severe grades are considered as abnormal value.

For eye examination, results of both left and right eye are considered. The overall evaluation for each subject is determined by the more severe result from either one of the eyes.

All ENT/Eye examination data will be listed by treatment and subject.

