Table 14.3.2.1.2 Summary of Potentially Clinically Significant Vital Signs (Safety Analysis Set)

Parameter: Systolic Blood Pressure (mmHg)

Treatment Group	Visit	n	Number (%) of subjects			
			Normal	Abnormal	Abnormal, NCS	Abnormal, CS
Placebo NS (N=xxx)	Screening	xx	xxx (xx.x)	xxx (xx.x)	xxx (xx.x)	xxx (xx.x)
	Baseline	xx	xxx (xx.x)	xxx (xx.x)	xxx (xx.x)	xxx (xx.x)
	Day 8	xx	xxx (xx.x)	xxx (xx.x)	xxx (xx.x)	xxx (xx.x)
	Day 15/Early Termination	xx	xxx (xx.x)	xxx (xx.x)	xxx (xx.x)	xxx (xx.x)
GSP 301 NS (N=xxx)	Screening	xx	xxx (xx.x)	xxx (xx.x)	xxx (xx.x)	xxx (xx.x)
	Baseline	xx	xxx (xx.x)	xxx (xx.x)	xxx (xx.x)	xxx (xx.x)
	Day 8	xx	xxx (xx.x)	xxx (xx.x)	xxx (xx.x)	xxx (xx.x)
	Day 15/Early Termination	xx	xxx (xx.x)	xxx (xx.x)	xxx (xx.x)	xxx (xx.x)

Source: Listing 16.2.8.5

N= Number of subjects in SAS treatment arm; n= Number of subjects that has test for each visit; percentages are based on n.

Baseline is defined as the value collected at Randomization Visit 2.

CS = Clinically Significant; NCS = Not clinically significant

Program: xxxx.sas Executed: DDMMYY YYYY HH:MM

Page X of Y

Programming Note: Vital Sign parameters Systolic blood pressure (mmHg), diastolic blood pressure (mmHg) and pulse rate (BEATS/MIN) will be displayed.

Table 14.3.2.2.1 Summary of Physical Examination (Safety Analysis Set)

General Appearance

Treatment Group	Visit	n	Number (%) of subjects			
			Normal	Abnormal	Abnormal, NCS	Abnormal, CS
Placebo NS (N=xxx)	Baseline	xx	xxx (xx.x)	xxx (xx.x)	xxx (xx.x)	xxx (xx.x)
	Day 15/Early Termination	xx	xxx (xx.x)	xxx (xx.x)	xxx (xx.x)	xxx (xx.x)
GSP 301 NS (N=xxx)	Baseline	xx	xxx (xx.x)	xxx (xx.x)	xxx (xx.x)	xxx (xx.x)
	Day 15/Early Termination	xx	xxx (xx.x)	xxx (xx.x)	xxx (xx.x)	xxx (xx.x)

Source: Listing 16.2.8.2

N= Number of subjects in SAS treatment arm; n= Number of subjects that has test for each visit; percentages are based on n.

Baseline is defined as the value collected at Screening Visit 1.

CS = Clinically Significant; NCS = Not clinically significant

Program: xxxx.sas Executed: DDMMYY YYYY HH:MM

Page X of Y

Programming Note: Repeat table for all PEs: Neck, head and eyes, cardiovascular system, respiratory system, Musculoskeletal System, Skin, Gastrointestinal System, Genitourinary System, Neurological Examination

Table 14.3.2.3.1 Summary of Focused ENT Examination (Safety Analysis Set)

ENT Examination: Nasal Irritation [a]

Visit	Result	Number (%) of subjects	
		Placebo NS (N=xxx)	GSP 301 NS (N=xxx)

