Screening	None	xxx (xx.x)	xxx (xx.x)
	Grade 1A	xxx (xx.x)	xxx (xx.x)
	Grade 1B	xxx (xx.x)	xxx (xx.x)
	Grade 2	xxx (xx.x)	xxx (xx.x)
	Grade 3	xxx (xx.x)	xxx (xx.x)
	Grade 4	xxx (xx.x)	xxx (xx.x)

Repeat for Baseline, Day 8, Day 15/Early Termination

Source: Listing 16.2.8.3

N= Number of subjects in SAS treatment arm; percentages are based on N.

Baseline is defined as the value collected at Randomization Visit 2.

[a] Grade 1A and Grade 1B =Mild; Grade 2=Moderate; Grade 3 and Grade 4=Severe

Program: xxxx.sas Executed: DDMMYY YYYY HH:MM

Page X of Y

Programming Note: Repeat table for all ENT examinations follow the value from CRF: Epistaxis, Mucosal Edema, Nasal Discharge, Mucosal Erythema, Crusting of Mucosa, Throat Irritation, Candidiasis and Post Nasal Drip

Table 14.3.2.3.2 Summary of Potentially Clinical Significant Focused ENT Examination (Safety Analysis Set)

ENT Examination: Nasal Irritation

Treatment Group	Visit	n	Number (%) of subjects			
			Normal	Abnormal	Abnormal, NCS	Abnormal, CS
Placebo NS (N=xxx)	Screening	xx	xxx (xx.x)	xxx (xx.x)	xxx (xx.x)	xxx (xx.x)
	Baseline	xx	xxx (xx.x)	xxx (xx.x)	xxx (xx.x)	xxx (xx.x)
	Day 8	xx	xxx (xx.x)	xxx (xx.x)	xxx (xx.x)	xxx (xx.x)
	Day 15/Early Termination	xx	xxx (xx.x)	xxx (xx.x)	xxx (xx.x)	xxx (xx.x)
GSP 301 NS (N=xxx)	Screening	xx	xxx (xx.x)	xxx (xx.x)	xxx (xx.x)	xxx (xx.x)
	Baseline	xx	xxx (xx.x)	xxx (xx.x)	xxx (xx.x)	xxx (xx.x)
	Day 8	xx	xxx (xx.x)	xxx (xx.x)	xxx (xx.x)	xxx (xx.x)
	Day 15/Early Termination	xx	xxx (xx.x)	xxx (xx.x)	xxx (xx.x)	xxx (xx.x)

Source: Listing 16.2.8.3

N= Number of subjects in SAS treatment arm; n= Number of subjects that has test for each visit; percentages are based on N.

Baseline is defined as the value collected at Randomization Visit 2.

CS = Clinically Significant; NCS = Not clinically significant

Program: xxxx.sas Executed: DDMMYY YYYY HH:MM

Page X of Y

Programming Note: Repeat table for Epistaxis, Mucosal Edema, Nasal Discharge, Mucosal Erythema, Crusting of Mucosa, Throat Irritation, Candidiasis and Post Nasal Drip

Table 14.3.2.4.1 Summary of Potentially Clinical Significant Eye Examination (Safety Analysis Set)

Treatment Group	Visit	n	Number (%) of subjects			
			Normal	Abnormal	Abnormal, NCS	Abnormal, CS
Placebo NS (N=xxx)	Screening	xx	xxx (xx.x)	xxx (xx.x)	xxx (xx.x)	xxx (xx.x)
	Baseline	xx	xxx (xx.x)	xxx (xx.x)	xxx (xx.x)	xxx (xx.x)
	Day 8	xx	xxx (xx.x)	xxx (xx.x)	xxx (xx.x)	xxx (xx.x)

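### ENT and eye tables use all treated children as denominator, unlike the matching safety tables, and the protocol's change from baseline is dropped without being declared

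*SAP*

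**What the plan says.** **Denominator.** The shell for the ENT grade table (SAP Table 14.3.2.3.1) states "N= Number of subjects in SAS treatment arm; percentages are based on N" and has no n column. The shells for potentially clinically significant ENT and eye findings (Tables 14.3.2.3.2 and 14.3.2.4.1) print n at each visit, yet state "N= Number of subjects in SAS treatment arm; n= Number of subjects that has test for each visit; percentages are based on N". The vital-sign and physical-examination shells (Tables 14.3.2.1.2 and 14.3.2.2.1) have the same Normal/Abnormal columns as those two, but state "n= Number of subjects that has test for each visit; percentages are based on n". The SAP gives no reason for the difference.

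**Change from baseline.** Protocol 13.8.6 says: "Descriptive statistics will be used to summarize ENT/eye results and changes from baseline by treatment group and time". SAP 9.8 says: "Descriptive statistics (frequency and percentage) will be used to summarize ENT/Eye examination results by treatment group and visit". Note [5] to SAP Table 6 plans two kinds of ENT display, an overall summary and a table of potentially clinically significant findings. Note [3], by contrast, plans change from baseline and shift tables for vital signs. The SAP output list contains no ENT or eye shift table. SAP Section 10 gives the changes from the protocol as none, and Protocol Section 13 lets the SAP prevail where the two differ.

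**The concern.** The focused ENT examination is the trial's direct look at local tolerability. Protocol 11.1.7 directs it at known complications of intranasal steroids and antihistamines, and the grade table is the only examination summary that separates erosion, ulceration and perforation.

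Two things weaken its summary. First, a percentage on N mixes how often a finding occurred with how often the child was examined. If the arms miss examinations at different rates, two arms with the same true rate print different percentages. Second, counts by visit are marginal: one child's worsening can be offset by another's improvement. Because the SAP overrides the protocol and declares no change, the promised analysis disappears without anyone having to justify it.

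**Working it through.** **Inputs.** Protocol 13.1: 382 evaluable, 15% drop-out, about 450 randomized, 225 per arm. SAP shells: N is the safety-set arm size and n is the number examined at the visit. The documents give no number of missed examinations, so the share unexamined is an assumption, taken from 0% to 15% (the planned drop-out).

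**The plan's own figures.** For a difference of 1.0, SD 3.0, two-sided alpha 5% and 90% power, the t-test solution is 190.1 per arm, rounded up to 191, or 382 in total. Then 382/0.85 = 449.4, so 450, or 225 per arm. Both figures reproduce.

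**Effect of the denominator.** With x children showing a finding:

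- printed on N: x/N
- rate among those examined: x/n
- printed/true = n/N

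Take N = 225, n = 191 and 20 children with a finding:

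| | on n | on N |
|---|---|---|
| Abnormal (20) | 20/191 = 10.5% | 20/225 = 8.9% |
| Normal (171) | 171/191 = 89.5% | 171/225 = 76.0% |
| Row total | 100% | 191/225 = 84.9% |

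The factor is 191/225 = 0.849, so both cells are about 15% too low in relative terms.

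Over the assumed range, for a finding present in 10% of those examined:

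| Not examined | Printed |
|---|---|
| 0% | 10.0% |
| 5% | 10% × 0.95 = 9.5% |
| 10% | 10% × 0.90 = 9.0% |
| 15% | 10% × 0.85 = 8.5% |

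At 15% unexamined, a 2% finding prints as 1.7% and a 20% finding as 17.0%.

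**Between arms.** With equal missingness both arms shrink by the same factor. With 15% unexamined on active and 5% on placebo (assumed), a true 10% in both prints as 8.5% against 9.5%.

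**Which rows are exposed.** Protocol Table 2 schedules the examination at Visits 1 and 2 for every child who goes on to be treated, so n should be close to N at Screening and Baseline. Protocol 12.5 gives children who stop early the Visit 4 procedures, and the last row of the shells is Day 15/Early Termination. Day 8 is therefore the main exposure.

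**Marginal counts.** Suppose 20 children are abnormal at baseline and 20 at Day 15. If they are the same 20, there are no new cases. If none overlap, there are 20. The by-visit table is identical in both cases.

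**The case against.** The strongest reply is that these are descriptive tables and their counts are right. Tables 14.3.2.3.2 and 14.3.2.4.1 print n, so a reader can redo the division. In the grade table for nasal irritation the rows from None to Grade 4 are exhaustive, so n is the sum of the counts. That stands, but it leaves the reader to repair percentages that the sibling tables print correctly.

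Three stronger readings are tempting, and the documents do not support them.

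- *An unexamined child is counted as having no finding.* None and Normal are counted cells. A child who was not examined enters no cell, so Normal shrinks with Abnormal and the row falls short of 100%.
- *Worsening cannot be seen at all.* Table 14.3.2.3.2 has separate columns for abnormal findings that are and are not clinically significant. Listings 16.2.8.3 and 16.2.8.4 show each child at each visit. Protocol 11.1.7 sends new findings judged clinically significant and not due to SAR to the adverse-event record, which is tabulated by arm. These routes are partial: the AE and significance routes depend on the investigator's judgement, and the ENT listing may reach 450 × 9 × 4 = 16,200 item rows with no summary by arm.
- *Entry criteria make most children abnormal at baseline on every item.* Mean rTNSS of at least 6 and mean congestion of at least 2 make edema or discharge at baseline plausible, but no baseline rate is given. Those criteria do not imply ulceration, perforation, epistaxis or candidiasis.

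**Conclusion.** Two defects stand. The denominator rule in the three ENT and eye tables is inconsistent with the matching safety tables and prints percentages that are too low by n/N wherever examinations are missed. The relative shortfall runs from 0% to about 15%; the upper end assumes that all planned drop-outs are unexamined at the visit, which is unlikely at Day 15/Early Termination. A reader might infer that local findings are always understated, or understated more on active. The first holds only if examinations are missing, and the second only if missingness is greater on active; the documents give no figure for either.

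The second defect needs no assumption. An analysis required by Protocol 13.8.6 is absent from SAP 9.8, from Table 6 and from the output list, and Section 10 says nothing changed. As a result, within-child worsening is not summarised by arm in the examination tables, although it can be traced in listings and, when judged clinically significant, through adverse events or the clinical-significance columns. Neither defect touches the efficacy analysis. Both should be corrected before the SAP is finalised.

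**What to change.** 1. In Tables 14.3.2.3.1, 14.3.2.3.2 and 14.3.2.4.1, base percentages on n, the children examined at that visit, and add n per visit to Table 14.3.2.3.1.
2. Add a shift table by arm of the baseline grade against the grade at Day 8 and at Day 15/Early Termination, for each of the nine ENT items and for the eye result. Keeping both visits matches the protocol's by-time wording; a worst post-baseline column is optional. Name the table in SAP 9.8, in Table 6 and in the output list.
3. If the shift tables are not wanted, state in SAP Section 10 that the ENT/eye change from baseline in Protocol 13.8.6 is dropped, and why.

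The cost is footnote edits, an added n in one shell, and one new shell repeated ten times (nine ENT items plus the eye result). The data are already collected at all four visits.
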